6. PROCEDURES

The following procedures/assessments will be conducted according to the schedule indicated in the Table of Events (Table 4).

6.1. Informed Consent

An Informed Consent Form (ICF) must be signed by the subject before any study-related assessments are performed. CCI

CCI Details of the informed consent process may be found in Section 14.3.

6.2. Contraception Education

The risks to a fetus or to a nursing child from apremilast are not known at this time. In animal studies, there were more miscarriages in female mice and monkeys who were given high doses of apremilast than in those who were not given apremilast. In addition, baby mice from the apremilast-treated mothers weighed less than normal baby mice. Results of the animal and in vitro studies can be found in the IB.

All females of childbearing potential (FCBP¹) must use one of the approved contraceptive options as described in Section 7.2 while on investigational product and for at least 28 days after administration of the last dose of the IP.

At the time of study entry, and at any time during the study when a FCBP's contraceptive measures or ability to become pregnant changes, the investigator will educate the subject regarding contraception options and correct and consistent use of effective contraceptive methods in order to successfully prevent pregnancy.

6.3. Medical and Disease History

Relevant medical history should be recorded, including caffeine consumption, smoking and alcohol history, as well as previous relevant surgeries. Disease history includes history of UC (ie, the disease under study).

6.4. Inclusion/Exclusion Criteria

Screening evaluations will be performed for all subjects to determine study eligibility. These evaluations are expected to be completed during the 28-day Screening Phase, prior to the date of the first dose of IP (study randomization). Subjects must meet all inclusion criteria (Section 7.2) and must not have any of the conditions specified in the exclusion criteria (Section 7.3) to qualify for participation in the study. Subjects may be allowed to re-screen upon discussion with the Sponsor. The subject's source documents must support his/her qualifications for the study

¹ A female of childbearing potential is a sexually mature female who 1) has not undergone a hysterectomy (the surgical removal of the uterus) or bilateral oophorectomy (the surgical removal of both ovaries) or 2) has not been postmenopausal for at least 24 consecutive months (that is, has had menses at any time during the preceding 24 consecutive months).

(eg, if a female subject does not require pregnancy testing and birth control because of a hysterectomy, the date of the hysterectomy must be included in the medical history).

6.5. Prior/Concomitant Medications and Therapies

All medications (prescription and nonprescription, including vitamins) taken by the subject up to 30 days prior to the Screening Visit (Visit 1) should be recorded, including the stop dates for medications prohibited in the study. All medications taken by the subject at any time during the study must also be recorded. Other key medications and therapies, such as previous treatment for tuberculosis or relevant diseases, should also be recorded.

6.6. Safety Assessments

6.6.1. Serum and Urine Pregnancy Tests for Females of Childbearing Potential

A serum pregnancy test with a sensitivity of ≤ 25 mIU/mL will be required for FCBP at screening. A urine pregnancy test will be performed on all FCBP at the Baseline Visit, Week 12, Week 52 and at all visits during the Extension Phase. In addition, a urine pregnancy test will be done at the Early Termination Visit. A urine pregnancy test kit will be provided by the central laboratory. Pregnancy tests should be performed if the FCBP has missed a menstrual period or the contraception method has changed.

6.6.2. Hepatitis B and C

The hepatitis screen includes testing for hepatitis B surface antigen and antibody, hepatitis B core antibodies (IgG/IgM), and antibodies to hepatitis C. Blood will also be drawn at screening for confirmatory hepatitis C testing to be completed for subjects who test positive for hepatitis C antibodies.

6.6.3. Vital Signs, Height, and Weight

Vital signs, including temperature, pulse, and seated blood pressure, will be taken during the visits indicated in Table 4. Height will be measured and recorded at screening; weight will also be measured and recorded at screening and then as indicated in Table 4. Body mass index (BMI) will be calculated at screening.

6.6.4. Complete and Limited Physical Examinations

Complete physical examinations will include evaluation of the skin, nasal cavities, eyes, ears, respiratory, cardiovascular, abdominal, neurological, lymphatic, and musculoskeletal systems. Limited physical examinations will include evaluation of the skin, respiratory, cardiovascular, lymphatic, and musculoskeletal systems. Results of the complete and limited physical examinations will be recorded only in the source documents.

Clinically significant abnormal findings (with the exception of the disease under study [UC]) identified prior to first dose of IP will be recorded on the electronic case report form (eCRF) as medical history; clinically significant findings after the first dose of IP will be recorded as AEs.

Note: Gynecological and urogenital examinations will not be performed unless for cause.

6.6.5. Vasculitis Assessment

The PDE4 inhibitors, including apremilast, have been shown to produce inflammatory perivascular histopathological changes in animal studies (eg, rodent toxicology studies). The investigator should be watchful for any signs and symptoms of vasculitis at all times. Any suspicion of vasculitis must be thoroughly investigated by taking pertinent patient history, doing a physical examination, reviewing AEs, and performing diagnostic procedures as clinically indicated. A subject with signs and symptoms of possible vasculitis should receive a thorough evaluation as described above, managed as medically appropriate, and continued with follow-up until the signs and symptoms of vasculitis have resolved.

6.6.6. Psychiatric Evaluation

Depression has been reported with the use of apremilast. Details are provided in the IB (Section 4.3.7.2.2).

The investigator should advise subjects, their caregivers, and families of the need to be alert for the emergence or worsening of depression, suicidal thoughts or other mood changes, and if such changes occur, to contact the investigator.

During the study (post randomization), any subject who is identified by the investigator (and/or appropriate site staff) as having a suicide attempt, or major psychiatric illness requiring hospitalization, must be immediately withdrawn from the study and referred for further medical and/or psychiatric care. If a subject is discontinued, the subject should return for the Post-treatment Observational Follow-up Visit after the Early Termination Visit.

At any time during the study (post randomization), the investigator (and/or appropriate site staff) should evaluate any subject who has thoughts of suicide to determine if the subject truly has suicide ideation. In such case, the subject will be referred to a psychiatrist for evaluation and treatment as appropriate. The subject may remain on IP until after the psychiatric evaluation, which should be completed within 3 weeks of the referral time. If the psychiatrist deems the subject not to be a risk for suicide, the subject may remain in the study, but if a risk of suicide is confirmed, the subject must be discontinued from the study. If the subject is discontinued, the subject should return for the Post-treatment Observational Follow-up Visit.

A copy of the psychiatric evaluation report must reside in the subject's source document.

6.6.7. Stool Culture / Microbiology

Stool culture analysis and assessment of *Clostridium difficile* toxin will be performed at the Screening Visit. A portion of the sample collected at screening will be retained for confirmatory testing to be completed for subjects who test positive for *Clostridium difficile* antigen. Subjects who are positive for *C. difficile* toxin may rescreen for the study after they have successfully completed therapy and had 2 months of consecutive negative tests for *C. difficile*.

6.6.8. Twelve-lead Electrocardiogram

The 12-lead ECG will be performed after the subject has been supine for approximately 3 minutes. Sites are to utilize their own local ECG machines for the study and the automated ECG readings will be further interpreted by the investigator by clinically correlating them with the subject's condition. The investigator's clinical interpretation will be recorded in the eCRF as:

normal; abnormal, not clinically significant; or abnormal, clinically significant. “Abnormal, clinically significant” results should be recorded in the Medical History eCRF if found prior to first dose of IP or in the AE eCRF if found after the first dose of IP.

6.6.9. Clinical Laboratory Evaluations

A central laboratory will be used for this study. Clinical laboratory evaluations will include:

- Hematology: complete blood count (red blood cell [RBC] count, hemoglobin, hematocrit, white blood cell [WBC] count and differential, absolute WBC counts, platelet count)
- Serum chemistries: total protein, albumin, calcium, phosphorous, glucose, total cholesterol, high-density lipoprotein cholesterol (HDL), low-density lipoprotein cholesterol (LDL), triglycerides, uric acid, total bilirubin, alkaline phosphatase, aspartate aminotransferase (AST)/serum glutamic-oxaloacetic transaminase (SGOT), alanine aminotransferase (ALT)/serum glutamic-pyruvic transaminase (SGPT), sodium, potassium, chloride, carbon dioxide, blood urea nitrogen (BUN), creatinine, lactic dehydrogenase (LDH), magnesium
- Urinalysis: dipstick urinalysis (specific gravity, pH, glucose, ketones, protein, blood, bilirubin, leukocyte esterase, nitrite, and urobilinogen)
 - Microscopic urinalysis (epithelial cells, RBC, WBC, and casts) will be performed only if the dipstick urinalysis is abnormal

Note: Clinical laboratory evaluations are not required to be fasting. However, the site will record whether a clinical laboratory evaluation was fasting or nonfasting on the lab requisition form.

6.6.10. Adverse Events

Adverse events (Section 11.1) will be recorded by the investigator from the time the subject signs informed consent to 28 days after the last dose of IP. The AEs, including SAEs, will be recorded on the AE page of the eCRF and in the subject’s source documents. All SAEs must be reported to Celgene Drug Safety within 24 hours of the investigator’s knowledge of the event by facsimile, or other appropriate method, using the SAE Report Form, or approved equivalent form. Worsening of a subject’s UC, including UC flare, should be considered as worsening of disease under study, and should not be captured as an AE. Worsening or exacerbation of UC, including UC flare, meeting the definition of an SAE should be reported as an SAE.

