4. OVERALL STUDY DESIGN

4.1. Study Design

This is a Phase 2, multicenter, randomized, double-blind, placebo-controlled, parallel-group, study to evaluate the efficacy and safety of 2 doses of apremilast in subjects with active UC (defined as a total Mayo score [TMS] of ≥ 6 to ≤ 11 , with an endoscopic subscore ≥ 2).

Approximately 165 subjects (55 subjects per arm) will be randomized in a 1:1:1 ratio using an Interactive Voice Response system (IVRS) or an Interactive Web Response System (IWRS) to receive oral apremilast (30 mg BID or 40 mg BID), or identically appearing placebo BID for up to 12 weeks, followed by 40 weeks of blinded treatment with apremilast (30 mg BID or 40 mg BID). At the end of 52 weeks in the study, subjects who have a Mayo endoscopy score ≤ 1 will have the opportunity to participate in the Extension Phase and will continue to receive apremilast for an additional 52 weeks.

Treatment assignment will be stratified via IVRS/IWRS based on concomitant use of oral corticosteroids and previous exposure to immunosuppressants (eg, 6-MP, AZA, or MTX). The number of subjects with previous exposure to immunosuppressants is targeted to comprise, no more than 50% of the subjects enrolled, and no less than 30%.

The study will consist of 5 phases:

- Screening Phase – up to 4 weeks
- Double-blind Placebo-controlled Phase – Weeks 0 to 12
- Blinded Active-treatment Phase – Weeks 12 to 52
- Extension Phase – Weeks 52 to 104
 - The 52-week extension is an active treatment phase and henceforth will be referred to as the Extension Phase for the remainder of the document. The Extension Phase was blinded prior to the implementation of Amendment 4. Following the implementation of Amendment 4, the Extension Phase will be open-label and all subjects will receive 30 mg BID as of their next visit.
- Post-treatment Observational Follow-up Phase – The 4-week period after the last dose of investigational product (IP).

Double-blind Placebo-controlled Phase

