In order to maintain the blind for the treatment assigned at baseline, all subjects will receive blister cards of identical appearance during the titration period beginning at Week 12. However, for subjects continuing on the dosage of apremilast assigned at baseline, and for subjects who are not undergoing dose titration (as noted above), the IP included in the “titration” portion of the blister card will include the total daily dose of apremilast (30 or 40 mg BID) and will not include the dose titration.

Extension Phase

At the end of the Blinded Active-treatment Phase (Week 52), subjects who have a Mayo endoscopy score ≤ 1 will have the opportunity to participate in the Extension Phase. Subjects participating in the Extension Phase will receive apremilast for an additional 52 weeks (ie, Weeks 52 to 104). Subjects entering the Extension Phase will receive apremilast 30 mg BID as of their next visit. Subjects currently in the Extension Phase who are receiving apremilast 40 mg BID will be switched to 30 mg BID at the next scheduled visit.

Post-treatment Observational Follow-up Phase

All subjects are required to spend 4 weeks in the Post-treatment Observational Follow-up Phase following the last dose of IP.

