5. TABLE OF EVENTS

Table 4: Table of Events

| | Screening Phase | Double-blind Placebo-controlled Phase | | | | | Blinded Active-treatment Phase | | | | | Extension Phase | | | ET | Post-treatment Observational Follow-up Phase |
|---|-----------------|---------------------------------------|--------------|--------------|--------------|----------------|--------------------------------|---------------|---------------|---------------|-----------------|-----------------|----------------|----------------|-----------------|--|
| Visit Number | 1 | 2 Baseline Visit | 3 | 4 | 5 | 6 ^a | 7 | 8 | 9 | 10 | 11 ^b | 12 | 13 | 14 | ET ^c | 15 ^d |
| Week | -4 to -1 | 0 (Day 1) | 2 (± 3 days) | 4 (± 3 days) | 8 (± 3 days) | 12 (± 3 days) | 16 (± 3 days) | 24 (± 3 days) | 36 (± 3 days) | 48 (± 3 days) | 52 (± 3 days) | 68 (± 7 days) | 86 (± 7 days) | 104 (± 7 days) | ET (± 3 days) | Obs. Follow-up (± 7 days) |
| Informed Consent | X | - | - | - | - | - | - | - | - | - | - | - | - | - | - | -- |
| Inclusion / Exclusion Criteria | X | X | - | - | - | - | - | - | - | - | - | - | - | - | - | - |
| Medical History | X | - | - | - | - | - | - | - | - | - | - | - | - | - | - | - |
| Prior / Concomitant Medications | X | X | X | X | X | X | X | X | X | X | X | X | X | X | X | X |
| Pregnancy Test and Contraception Education ^e | X | X | - | - | - | X | - | - | - | - | X | X | X | X | X | - |
| Hepatitis B and C Tests | X | - | - | - | - | - | - | - | - | - | - | - | - | - | - | - |
| Clinical Lab Evaluations | X | X | - | - | - | X | - | - | X | - | X | X | X | X | X | - |
| Stool Culture / Microbiology | X | - | - | - | - | - | - | - | - | - | - | - | - | - | - | - |
| Height | X | - | - | - | - | - | - | - | - | - | - | - | - | - | - | - |
| Vital Signs / Weight | X | X | X | X | X | X | X | X | X | X | X | X | X | X | X | X |
| Complete Physical Exam | X | - | - | - | - | X | - | - | - | - | X | - | - | X | X | - |
| Limited Physical Exam | - | X | - | - | - | - | - | X | - | - | - | X ^f | X ^f | | - | X |
| Adverse Events ^g | X | X | X | X | X | X | X | X | X | X | X | X | X | X | X | X |

Table 4: Table of Events (Continued)

| Visit Number | Screening Phase | Double-blind Placebo-controlled Phase | | | | | Blinded Active-treatment Phase | | | | | Extension Phase | | | ET | Post-treatment Observational Follow-up Phase |

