| SF-12v2 (Short Form 12-item Health Survey, version 2) | - | X | - | - | - | X | - | - | - | - | X | - | - | X | - | - |
| CCI | | | | | | | | | | | | | | | | |
| Dispense IP | - | X | X | X | X | X | X | X | X | X | X | X | X | X | - | - |
| Return and Count IP | - | - | X | X | X | X | X | X | X | X | X | X | X | X | X | - |

ECG=Electrocardiogram; ET= Early Termination Visit; CCI [redacted]; IP = Investigational Product; Obs. Follow-up=Post-treatment Observational Follow-up Phase; CCI [redacted]; PGA= Physicians Global Assessment; PMS= Partial Mayo Score; TMS= Total Mayo Score; UC= ulcerative colitis.

- ^a Subjects will be evaluated based on the TMS at the Week 12 Visit and will receive blinded active IP for an additional 40 weeks (Section 4.1).
- ^b At the Week 52 Visit, subjects who have a Mayo endoscopy score ≤1 will have the opportunity to participate in an Extension Phase and will receive apremilast 30 mg BID. With the implementation of Amendment 4, subjects currently in the Extension Phase who are receiving apremilast 40 mg BID will be switched to 30 mg BID at the next scheduled visit.
- ^c Subjects who discontinue from the study prior to the Week 52 Visit, or prior to the Week 104 Visit for subjects participating in the Extension Phase, will have the Early Termination Visit. Subjects who complete the Week 52 Visit and do not participate in the Extension Phase will not have the Early Termination Visit.
- ^d The Post-treatment Follow-up Visit will be conducted approximately 4 weeks after the last dose of IP for all subjects.
- ^e The female subject's chosen form of contraception must be effective by the time the female subject is randomized into the study (for example, hormonal contraception should be initiated at least 28 days before randomization). Contraception education is for males and Females of Child Bearing Potential (FCBP). Pregnancy testing will be performed 7 times during the study for FCBP. Serum pregnancy tests will be performed at Screening and urine pregnancy testing will be done at the Baseline Visit, Week 12, Week 52 (or at the Early Termination Visit if prior to the Week 52 Visit) and all visits during the Extension Phase. In addition, urine pregnancy testing will be done at the Early Termination

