11. ADVERSE EVENTS

11.1. Monitoring, Recording and Reporting of Adverse Events

An adverse event (AE) is any noxious, unintended, or untoward medical occurrence that may appear or worsen in a subject during the course of a study. It may be a new intercurrent illness, a worsening concomitant illness, an injury, or any concomitant impairment of the subject's health, including laboratory test values (as specified by the criteria in Section 11.3), regardless of etiology. Any worsening (ie, any clinically significant adverse change in the frequency or intensity of a pre-existing condition) should be considered an AE. A diagnosis or syndrome should be recorded on the AE page of the eCRF rather than the individual signs or symptoms of the diagnosis or syndrome.

Abuse, withdrawal, sensitivity or toxicity to an investigational product should be reported as an AE. Overdose, accidental or intentional, whether or not it is associated with an AE should be reported on the drug exposure eCRF page. (See Section 8.6.1 for the definition of overdose.) Any sequela of an accidental or intentional overdose of an investigational product should be reported as an AE on the AE eCRF. If the sequela of an overdose is an SAE, then the sequela must be reported on an SAE report form and on the AE eCRF. The overdose resulting in the SAE should be identified as the cause of the event on the SAE report form and eCRF but should not be reported as an SAE itself.

All subjects will be monitored for AEs during the study. Assessments may include monitoring of any or all of the following parameters: the subject's clinical symptoms; weight loss; diarrhea; laboratory; pathological; radiological or surgical; findings; physical examination findings; or findings from other tests and / or procedures.

All AEs will be recorded by the Investigator from the time the subject signs informed consent until 28 days after the last dose of IP and those SAEs made known to the investigator at any time thereafter that are suspected of being related to IP. Adverse events and SAEs will be recorded on the AE page of the CRF and in the subject's source documents. All SAEs must be reported to Celgene Drug Safety within 24 hours of the Investigator's knowledge of the event by facsimile, or other appropriate method, using the SAE Report Form, or approved equivalent form.

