11.4.1. Females of Childbearing Potential

Pregnancies and suspected pregnancies (including a positive pregnancy test regardless of age or disease state) of a female subject occurring while the subject is on IP, or within 28 days of the subject's last dose of IP, are considered immediately reportable events. Investigational product is to be discontinued immediately. The pregnancy, suspected pregnancy, or positive pregnancy test must be reported to Celgene Drug Safety immediately by facsimile, or other appropriate method, using the Pregnancy Initial Report Form, or approved equivalent form.

The female subject may be referred to an obstetrician-gynecologist or another appropriate healthcare professional for further evaluation.

The investigator will follow the female subject until completion of the pregnancy, and must notify Celgene Drug Safety immediately about the outcome of the pregnancy (either normal or abnormal outcome) using the Pregnancy Follow-up Report Form, or approved equivalent form.

If the outcome of the pregnancy was abnormal (eg, spontaneous abortion), the investigator should report the abnormal outcome as an AE. If the abnormal outcome meets any of the serious criteria, it must be reported as an SAE to Celgene Drug Safety by facsimile, or other appropriate method, within 24 hours of the investigator's knowledge of the event using the SAE Report Form, or approved equivalent form.

All neonatal deaths that occur within 28 days of birth should be reported, without regard to causality, as SAEs. In addition, any infant death after 28 days that the investigator suspects is related to the in utero exposure to the IP should also be reported to Celgene Drug Safety by facsimile, or other appropriate method, within 24 hours of the investigator's knowledge of the event using the SAE Report Form, or approved equivalent form.

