- The APR 30 BID group includes the data during the APR 30 BID treatment for subjects who receive APR 30 BID only in the study, subjects who initially receive APR 30 BID and switch to APR 40 BID at Week 12, and subjects who initially receive placebo and switch to APR 30 BID at Week 12.
- The APR 40 BID group includes the data during the APR 40 BID treatment for subject who receive APR 40 BID only in the study and subjects who initially receive placebo and switch to APR 40 BID at Week 12.
- The APR 30 BID/APR 40 BID group includes the data during the APR 40 BID treatment for subjects who initially receive APR 30 BID and switch to APR 40 BID at Week 12.
- The APR total group combines all the data of all the groups.

For the summaries of labs, vital signs, and body weight by time point, the data during the APR 30 BID and APR 40 BID treatments after Week 12 for subjects who initially receive

placebo and switch to APR 30 BID and APR 40 BID, respectively, at Week 12 will be summarized in the placebo/APR 30 BID and placebo/APR 40 BID groups, respectively.

- Weeks 0-104 apremilast-exposure period: This period encompasses all apremilast-exposure data through Week 104, irrespective of when the apremilast exposure starts (at Week 0 or 12) in the study. It starts on the date of the first dose of apremilast in the study, and ends 28 days after the last dose of apremilast in the study or on the date of the actual last follow-up in the study, whichever comes first.

Of note, this period is exclusive of the date of the first dose of apremilast in the study for the analyses of the lab, vital signs, weight, and ECG data.

The treatment groups presented in the safety analysis tables for the apremilast-exposure period during Weeks 0-104 will be the same as those for the apremilast-exposure period during Weeks 0-52.

- Weeks 52-104 apremilast-exposure period: This period encompasses the apremilast-exposure data during Weeks 52-104 and is to be summarized for subjects who receive at least 1 dose of apremilast after Week 52 (defined as the date of the last dose of apremilast in the study no earlier than the date of IP dispensing at Week 52). It starts on the date of IP dispensing at Week 52, and ends 28 days after the last dose of apremilast in the study or on the date of the actual last follow-up in the study, whichever comes first.

Of note, this period is exclusive of the date of IP dispensing at Week 52 for the analyses of the lab, vital signs, weight, and ECG data.

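### Visit 15 may take place on Day 21 after the last dose, so up to 7 of the 28 days of AE collection can pass with no scheduled contact

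*Protocol*

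**What the plan says.** Protocol 6.6.10 has AEs recorded "from the time the subject signs informed consent to 28 days after the last dose of IP". Section 11.1 repeats the limit, "until 28 days after the last dose of IP and those SAEs made known to the investigator at any time thereafter", with the later SAEs restricted to those suspected of being related to IP; 11.5 agrees. Pregnancies (11.4.1) occurring on IP or "within 28 days of the subject's last dose of IP, are considered immediately reportable events".

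Protocol 4.1 defines the follow-up phase as "The 4-week period after the last dose of investigational product (IP") and adds: "All subjects are required to spend 4 weeks in the Post-treatment Observational Follow-up Phase following the last dose of IP".

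Table 4 heads the column for Visit 15 "Obs. Follow-up (± 7 days"), and its footnote d reads "The Post-treatment Follow-up Visit will be conducted approximately 4 weeks after the last dose of IP for all subjects". Visit 15 is the last column. The one telephone row in Table 4 is a diary reminder before visits. An Early Termination Visit, where there is one, comes before Visit 15.

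SAP 5.2 treats data inside the defined safety periods as treatment-emergent. For the Weeks 0-104 period, and likewise the Weeks 52-104 period, the period "ends 28 days after the last dose of apremilast in the study or on the date of the actual last follow-up in the study, whichever" is earlier. The same rule applies to subjects who stop by Week 12 or Week 52 in the periods that end there. SAP 12.1.2 plans a summary of TEAEs from the last dose to 28 days after it, without an exposure-adjusted incidence rate (EAIR). SAP Table 2 counts follow-up as completed when the visit is completed, whatever the day.

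**The concern.** The collection period and the visit that serves it do not match. Elsewhere in the schedule a symmetric window does little harm, because the next visit picks up whatever an early attendance missed. After Visit 15 nothing does. A subject seen on Day 21 is within window, yet a quarter of the post-dose period is still to come and no one is scheduled to ask about it.

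Safety and long-term safety are the two secondary objectives that are not redacted. An event on Days 22-28 may go unreported because the subject is not asked. If it is reported, the SAP rule may still leave it out of the treatment-emergent set. The post-treatment table, labelled as running to 28 days, would then give equal weight to subjects observed for 21 days and for 28.

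**Working it through.** **Inputs.**
- AE collection to 28 days after the last dose: Protocol 6.6.10, 11.1, 11.5.
- Follow-up phase of 4 weeks: Protocol 4.1.
- Visit 15 at about 4 weeks, ± 7 days: Protocol Table 4 and footnote d.
- End of safety period at the earlier of Day 28 and actual last follow-up: SAP 5.2.
- 165 subjects and 10% dropout before Week 12: Protocol 10.3.

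**1. The plan's own figure.** 4 weeks × 7 = 28 days. The phase length and the collection period agree with each other; the visit window is what departs from them.

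**2. Permitted visit days.** 28 − 7 = Day 21 and 28 + 7 = Day 35. That is 35 − 21 + 1 = 15 permitted days, of which Days 21 to 27 (7 days) precede the end of collection.

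**3. Largest gap within window.** 28 − 21 = 7 days, and 7 / 28 = 25% of the post-dose period. This needs no assumption.

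**4. How many subjects.** The documents do not say when visits took place. A subject seen before Day 28 loses 1 to 7 days and any other attendee loses none, so the in-window average over all attendees could lie anywhere from 0 to 7 days. If visits were spread evenly over Days 21-35, 7 / 15 = 47% would be early, with a mean loss of (7+6+5+4+3+2+1) / 7 = 4 days among them. That is an illustration only.

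**5. What the SAP does with the gap.** Take a visit on Day 21 and an AE starting on Day 25 that the subject volunteers.
- Protocol 6.6.10 requires it to be recorded.
- Under SAP 5.2 the safety period closed on Day 21, so the event is not treatment-emergent and drops out of the 12.1.2 post-treatment table. This takes the actual last follow-up to be the Visit 15 date. The SAP text available does not define the term; if a later spontaneous contact counted as follow-up, the event would stay in.
- Under SAP 12.1 the exposure time of a subject without the event is the duration of the period, so Days 22-28 also leave the EAIR denominator. That denominator is not inflated.

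**6. Share of the safety period.** For a subject on apremilast from Week 0:
- stopping at Week 52: 52 × 7 + 28 = 392 days, and 7 / 392 = 1.8%;
- completing Week 104: 104 × 7 + 28 = 756 days, and 7 / 756 = 0.9%.

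The share is larger with shorter exposure. For a subject who stops at Week 12 it is 7 / (84 + 28) = 6.3%.

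**7. The placebo-controlled comparison.** For subjects who continue past Week 12, the Weeks 0-12 period ends before Week 12 dispensing, so Visit 15 plays no part. At the planned dropout, 0.10 × 165 = 16.5, so about 16 or 17 subjects could be affected across the three arms.

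**The case against.** The best reply is that the two rules govern different things. The window says when a visit may occur; the 28 days say how long events are recorded. A reader might infer that a site may close a subject out on Day 21 and remain compliant. The documents do not support that: the recording duty and the required 4 weeks in follow-up both continue, and a site that stopped recording on Day 21 would breach the protocol. This part of the objection stands, and it confines the point to active ascertainment.

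A reader might also infer that pregnancies, UC flares or late mood changes are being missed. The support is thin.
- Table 4 has no pregnancy test at Visit 15, and pregnancy reporting is immediate and triggered by the event.
- A non-serious flare is not captured as an AE at all, and a serious one is reportable within 24 hours of the investigator's knowledge.
- No legible text describes a mood effect appearing after withdrawal, and 6.6.6 already has subjects and families told to contact the investigator.

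The SAP's earlier-of rule is partly protective, because it keeps unobserved days out of person-time. That stands too, but it does not recover missed events and does not help the crude post-treatment table. That table is descriptive, since SAP 12 plans no inferential safety testing.

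Finally, the protocol gives a terminal half-life of about 6 to 9 hours, so Day 21 is at least 21 × 24 / 9 = 56 half-lives after the last dose and drug-related events that late may be few. That bears on how much is lost, but the sponsor chose 28 days in several sections and the schedule should be able to deliver it.

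**Conclusion.** The point holds as a modest mismatch between the visit schedule and the collection period. At most 7 of the 28 post-dose days lack scheduled ascertainment, for a subject seen at the early edge of the window. The number of such subjects is unknown. The 47% figure should not be read as an estimate, because it rests on an even spread of visits that nothing in the documents supports.

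Two consequences follow in the analysis: an AE on Days 22-28 can be recorded yet not counted as treatment-emergent, and crude post-treatment incidence can be understated. Both rest on taking Visit 15 as the actual last follow-up.

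The effect is confined to the post-treatment tail. It reaches the placebo-controlled safety comparison only through subjects who stop by Week 12 and leaves the Week 12 primary endpoint untouched. It is worth correcting because the correction is cheap, not because the safety conclusions are in danger.

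**What to change.** Reconcile the Visit 15 window with the 28-day collection period. In Protocol Table 4, change the window from ± 7 days to 0 to +7 days, and have footnote d say that the visit takes place at least 28 days after the last dose of IP. The SAP's 28-day limit then applies to everyone who attends within window, and its text can stay as it is.

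The cost is scheduling flexibility: 8 permitted days (Days 28 to 35) instead of 15. No visit or procedure is added. Where that is too tight, an AE telephone contact on or after Day 28 would also close the gap, at the price of one extra contact.

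Protocol 4.1.2 states that with Amendment 4 all subjects will be in the Extension Phase, so the change helps only those whose follow-up is still ahead. For subjects already seen before Day 28, report the follow-up days actually observed alongside the post-treatment TEAE table in SAP 12.1.2.
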